participant expresses suicidal or homicidal ideation (SI and HI, respectively), study staff will respond using a standard of practice that has been used successfully in our lab's past telehealth-based trials. The study staff member responsible for the call will be instructed to gather more information from the participant, including information about plan, means, intent, intended victim (in the case of HI) and history of suicidal and homicidal behavior. Any participant who expressed SI will be provided with the suicide hotline number. The participant will be informed that the PI may contact him/her to talk more about his/her SI or HI. The study coordinator will obtain current contact information for the participant and inform the PI, who will contact the participant as necessary to ensure participant safety. In cases of imminent homicidality or suicidality, which are not anticipated, we will seek guidance from the Psychiatric Emergency Clinic on best strategies for follow-up, which could include, but is not limited to, self-presentation at the VA's emergency room with the help of an emergency contact, calling 911, or calling local police for a wellness check.

Data Analysis and Statistical Considerations

Stage/Aim 1: Content analysis of the qualitative interviews will be conducted according to methods described by Zhang and Wildemuth (2016). Data will be analyzed in two phases. Initially, there will be a conventional content analysis, followed by an inductive, thematic approach to identify patterns. Coded data will be analyzed for patterns and themes. Data management and coding will use ATLAS ti software (Muhr, 2004). With our total sample size across both cohorts (N =10), we estimate that we will be able to identify and address 95% of usability problems in the MIRA intervention application (Faulkner, 2003).

As well as improving app usability, data analysis and interpretation will be primarily focused on themes of: 1) session dose, timing, and frequency; and 2) treatment engagement/adherence. For example, if the majority of participants report that 5 sessions of treatment a week is too frequent or that they do not think that a 10-minute treatment session is long enough, we will adjust the treatment accordingly. We will also incorporate quantitative data (e.g., on average how many sessions participants complete) into these decisions.

We will also conduct a qualitative analysis of the weekly anger and hostile interpretation bias data by graphing these measures across time for each participant to determine if and when these measures decrease, as this will help us to determine whether there is an optimal dose of treatment and number of treatment sessions across participants.

In order to analyze descriptive data from the qualitative interviews, we will need access to NVivo 11 software, which is not available through VINCI. Therefore, deidentified data (with none of the 18 HIPAA identifiers or the study ID) will be moved to Duke University Medical Center for analysis. Only fully deidentified data will be stored on Duke computers. Any data movement to Duke will be accomplished using email. Any data transfer from Duke machine(s) back to VA will also be done via email. Data will be stored at Duke on a protected server to which only [name] and her study staff have access; data are encrypted at rest.

Research Protocol, Version Date: 7/28/2022

Page 14 of 23

Stage/Aim2: Recognizing that it is inappropriate to examine efficacy in a small pilot trial, we will focus on feasibility and acceptability objectives (Leon et al., 2011). As appropriate for this stage of treatment development and evaluation, analysis and interpretation will focus on describing the primary outcomes: acceptability of the intervention and feasibility of the trial approach. We will examine the recruitment rate, treatment retention, patient satisfaction, and app utilization as primary outcomes.

We will also describe Nightly Diary outcomes, including: daily emotions and pain reported; how helpful the app was; whether it made them feel differently about things that happened during their day. Additionally, although we will not be able to statistically analyze group differences, we will describe group differences in clinical (anger-related) outcomes and functional outcomes, including whether changes were observed in the expected directions (reductions in anger variables and increases in functional outcomes).

Finally, mixed between-within repeated measures ANOVA will be used to examine potential treatment effects on overall HRV. Specifically, 2 (Treatment) X 2 (Time) ANOVAs will be used to model SDNN, LF, and HF to determine whether overall HRV increases from pre- to post-treatment as a result of IBM relative to the control condition. We will also examine changes from pre- to post-treatment in physiological reactivity to anger. Using methodology that we have applied to examine mood-related autonomic arousal (e.g., Dennis et al., 2017), we will use multilevel modeling (MLM) to examine short-term changes in HRV and HR associated with momentary assessments of anger. MLM is appropriate for analyzing unbalanced repeated-measures data and can incorporate both person-level predictors (e.g., treatment condition) and episodic predictors (e.g., anger; . We will thus examine whether the association between anger and autonomic arousal (i.e., HR, SDNN, LF, and HF) attenuates following treatment, particularly for participants assigned to the MIRA condition. We will also examine whether this expected decrease in autonomic reactivity is associated with improved functional outcomes and decreased anger outcomes.

Privacy, Confidentiality, and Information Security

1. Lists of Data Reviewed and/or Collected for Screening/Recruitment and Conduction of Study:

The Personal Health Information that will be obtained, used, and/or shared for this study includes:

Identifier(s)	Source(s) of Health Information
Names	Medical history & physical exam
	information
All geographic subdivisions smaller than	igert Photographs, videotapes, audiotapes,
a State, including street address, city,	or digital or other images
county, precinct, and zip code. Describe:	
Participants' addresses will be collected	
during the study in order to pay them for	
participation.	

Identifier(s)	Source(s) of Health Information
All elements of dates (except year) for	Biologic specimens (e.g., blood,
dates directly related to an individual,	tissue, urine, saliva). Describe:
including birth date, admission date,	, , , , , , , , , , , , , , , , , , , ,
discharge date, visit or treatment dates, etc.;	
and all ages over 89, Describe: Date of	
participation will be collected. In addition,	
treatment records, laboratory results, etc.	
will be collected.	
Telephone numbers	
Fax numbers	Diagnostic / Laboratory test results
Electronic mail addresses	Operative reports
Social Security Numbers	Imaging (x-ray, CT, MRI, etc.)
Medical record numbers	Discharge summaries
Health plan beneficiary numbers	Survey / Questionnaire responses
Account numbers	Billing records
Certificate and/or license numbers	HIV testing or infection records
Vehicle identifiers and serial numbers,	Sickle cell anemia information
including license plate numbers	
Device identifiers and serial numbers	Alcoholism or alcohol use information
Web Universal Resource Locators	igert Drug abuse information
(URLs)	
Internet Protocol (IP) address numbers	igert Mental health (not psychotherapy)
	notes
Biometric identifiers, including finger &	Psychological test results
voice prints	
Full-face photographic images and any	Genetic testing
comparable images	
Any other unique identifying number,	Other, describe:
linked study ID, characteristic, or code,	
describe: study ID number	
2. Data and/or Specimen Acquisition:	la a al a III de ada a santa A
Data for this study will be collected through (c	
Prospective data and/or specimen collecti	
description of processes: Data will be obtained	
semi-structured interviews, and app utilization Retrospective data collection and/or specific	
data access. Describe how data will be obtain	
accordance with a Waiver or Alteration of HIP	
telephone numbers, social security numbers,	·
participants will be obtained from the VA's Re	
Retrospective data collection and/or speci	•
data and/or specimen repository. Indicate the	• • •
location, and IRB number:	

Research Protocol, Version Date: 7/28/2022

Note: for data and/or specimens obtained from a VA approved data repository, a Data Use Agreement (DUA) must be executed prior to obtaining data and/or specimens. See VHA Handbook 1200.12 for further information.

3.	Level of Data:
Th	e following level(s) of data will be acquired/maintained for this study (check all that
арі	oly):
\times	Identified (e.g., names, addresses or other identifiers included)
X	Coded (direct and/or all identifiers removed, but study code/ID included)
X	De-Identified (all HIPAA 18 and study ID/code removed):
	Verified Statistically
	OR
	∇erified by Absence or Removal of HIPAA 18 and study ID
	Limited Data Set
	Other: Describe:

4. Location of Data and/or Specimens, and Data Retention Plan:

A. Data and/or Specimen Location: Data will be stored electronically in \\ VHADURFPC02B\groups1\Nicotine Research\Study Information\Study Logbooks\ [name] CDA and \\VHADURFPC02B\groups1\Nicotine Research\Study Information\ Study Databases\[name] CDA. Data that will be stored electronically include name, address, phone number, social security number, amount of study payment earned, and date of visits (in Study Logbooks location). The study logbook will contain the key connecting PHI and the study identification number. Paper records of data include study consent form and HIPAA authorization (identified), questionnaire responses, and interview notes (coded). Audio recordings of interviews will be captured using an Olympus VN-722PC. When not in use, the audio recorder will be stored in a locked file cabinet in our study offices at building 1, Durham VA Medical Center. Recordings will be moved from the audio recorder to the "Study Logbooks" location listed above; our laboratory has sanctuary exemption to allow these devices to plug into the network, as they are used in other current research projects. For long term storage, audio recordings may be moved to an encrypted DVD that is password-protected. Any encrypted DVDs will be stored in a locked filing cabinet in a locked office. Transcriptions from the study interviews will be stored electronically at the Study Logbooks location listed above. Study data collected via a Duke IRB protocol will be combined with VA data. Data will be transferred via a VA-owned FIPS-encrypted thumbdrive or via VA's S.A.F.E.

 \boxtimes Data will be also be placed at the VA Informatics and Computing Interface (VINCI; http://vaww.vinci.med.va.gov/vincicentral/VINCIWorkspace.aspx). The VA Informatics and Computing Infrastructure is a partnership between the VA Office of Information Technology and the Veterans' Health Administration Office of Research and Development. Researchers and operations staff can use VINCI to access data and statistical analysis tools in a virtual working environment through a certified VHA network computer using the VA Intranet or Virtual Private Network (VPN). B. Data Retention Plan

Mobile Intervention for Problematic Anger

Research records will be maintained and destroyed according to the National
Archives and Records Administration, Records Schedule Number: DAA-0015-2015-
0004. Records destruction, when authorized, will be accomplished using the then
current requirements for the secure disposal of paper and electronic records. Currently,
destruction of research records (see DAA-0015-2015-0004, section 7.6 "Research
Investigator Files" for materials included in research records) is scheduled for 6 years
after the cut-off (the cut-off is the completion of the research project) and may be
retained longer if required by other federal agencies. Records will not be destroyed
without pre-notification to the facility records manager.
Other data retention plan, describe:

5. Data Access and Data Recipients: Only members of our DVAMC research team will have access to identifiers and coded data. In order for data analysis to occur using NVivo 8, ATLAS.ti, and SAS software, a de-identified dataset will be uploaded to VINCI for analysis using VA-owned data analysis software (NVivo 8).

In order to analyze descriptive data from the qualitative interviews, we will need access to NVivo 11 software, which is not available through VINCI. Therefore, deidentified data (with none of the 18 HIPAA identifiers or the study ID) will be moved to Duke University Medical Center for analysis. Any data movement to Duke will be accomplished using email. Any data transfer from Duke machine(s) back to VA will also be done via email. Data will be stored at Duke on a protected server to which only [name] and her study staff have access; data are encrypted at rest.

All VA research personnel who have access to VHA records are instructed, in accordance with VA policy, on the requirements of Federal privacy and information laws and regulations, VA regulations and policies, and VHA policy. All study personnel who are VA employees working within the VA system have fulfilled all required HIPAA and other VA security and privacy policy training requirements and have agreed to follow guidelines pertaining to the protection of patient data. All research staff sign VA Rules of Behavior, and all study staff are up-to-date with VHA Privacy Policy Training and the VA Office of Cyber and Information Security Awareness Training Course. The data security and privacy procedures summarized in that course include logging off or locking the computer when walking away from it; no sharing of access codes, verify codes or passwords; not allowing anyone else to use the computer under one's password; and disposing of sensitive information using VA-approved methods (e.g., shredder bins). Access to study data will be removed for all study personnel when they are no longer part of the research team.

Study visits will either be conducted at the main VA Hospital or at the MIRECC at Croasdaile, based on participant preference and space availability. Data that is transported between the main hospital and Croasdaile offices will be secured in a lockable briefcase.

6. Data and/or Specimen Transportation and/or Transmission for all data and/or specimens involved in the study:

Mobile Intervention for Problematic Anger

I.	Data and/or specimens will not be transported or transmitted outside of Durham VAMC environment.
II.	Data and/or specimens will be transported BETWEEN sites that are under the auspices of the Durham VA Medical Center.
III.	Data and/or specimens will be transmitted to other VA sites using the following method(s):
	 A. Data Data are de-identified and thus will be sent via unencrypted e-mail or unencrypted disk (encryption is optional). Data are coded or contain identifiers and thus will be sent Other, describe:
	 B. Specimens Specimens are de-identified and thus will be sent via standard carrier (tracking is optional). Specimens are coded or contain identifiers and thus will be sent via VA-
	authorized carrier with tracking. Other, describe:
	Data and/or specimens will be transported to non-VA/VHA sites (e.g., academic affiliates, laboratories, etc.) using the following method(s):
	A. Data
	Data are de-identified and thus will be sent via unencrypted e-mail or
	unencrypted CD. Data are coded or contain identifiers and thus will be sent via <chose 140-2="" as="" cd="" drive="" encrypted="" fips="" flash="" hard="" method="" of="" or="" such="" transfer=""> using VA—approved carrier with tracking. Data are coded or identified and will be uploaded to sponsor website using electronic case report form (eCRF) <insert including<="" information="" td=""></insert></chose>
	sponsor name and URL and the encryption the site uses.> Other, describe:
	B. Specimens
	 Specimens Specimens are de-identified and thus will be sent via standard carrier (tracking is optional) or will be hand-delivered by research study personnel. Specify method of delivery: Specimens are coded and thus will be sent via VA-approved carrier with tracking or will be hand-delivered by research study personnel. Specify
	method of delivery:
In acco	ordance with the HIPAA and the Privacy Act, for any coded or identifiable data or
specim an Acc spread the nat	nens released from the Durham VAMC (with the exception of Limited Data Sets), counting of Disclosure (AOD) will be maintained (e.g., in a database or Isheet) that includes the participant's name, date of the disclosure, description of ture of the Individually Identifiable Information (III) disclosed, purpose of each ture, and the name and address of the person/agency to whom the disclosure
	C. Local DVAMC memorandum "Authorization to Use, Process, Store, or Transmit VA Sensitive Information Outside VA Owned or Managed Facilities" has

Research Protocol, Version Date: 7/28/2022

been pre-filled out for each study team member who may transport the data and/ or specimens off-site. This (these) forms are included with the IRB materials.
D. Containers (e.g., briefcase, bin) are labeled with the following notice (label placed on the outside of container) in accordance with VHA Directive 6609: NOTICE!!!
Access to these records is limited to: AUTHORIZED PERSONS ONLY. Information may not be disclosed from this file unless permitted by all applicable legal authorities, which may include the Privacy Act; 38 U.S.C. §§ 5701, 5705, 7332; the Health Insurance Portability and Accountability Act; and regulations implementing those provisions, at 38 C.F.R. §§ 1.460 – 1.599 and 45 C.F.R. Parts 160 and 164. Anyone who discloses information in violation of the above provisions may subject to civil and criminal penalties.
 7. Risk Mitigation Strategies: Data are fully de-identified (stripped of HIPAA 18 and study ID/code) before being shared outside of Durham VAMC. Specimens are fully de-identified (stripped of HIPAA 18 and study ID/code before being shared outside of Durham VAMC. Direct identifiers will be maintained separately from data and or specimens by using a code to "identify" subjects. In a separate database (i.e., a "linking" or "cross-walk" database) this code will be linked to identifying subject information. Other, specify:
8. Suspected Loss of VA Information: Should any incident such as theft or loss of data, unauthorized access of sensitive data or non-compliance with security controls occur it will be immediately reported according to VA policy. All incidents regarding information security/privacy incidents will be reported to the ISO and PO within 1 hour of acknowledgement of issue and done so using the VHADUR Research Events Report e-mail group ([contact]).
 9. Reporting of Results: Reporting of results, such as in scientific papers and presentations, will never identify individual subjects. Data will be presented in aggregate and individual-level data will not be published. Other results reporting plan, describe:
10. Future Use of Data: ☐ Data will be retained for future use. This is described elsewhere in the protocol and is noted in the HIPAA authorization. ☐ Future Use of data is optional (i.e., not required by the research subject). ☐ Future Use of data is required for participation in the study. ☐ No future use of data is currently planned.
11. Use of Mail Merge Technology

Mobile Intervention for Problematic Anger

Mail merge programs will be used to generate letters and/or address labels for mailings to potential or already enrolled research subjects. The study team is aware that to reduce risk of mail merge related privacy incidents, use of mail merge programs requires a 25% accuracy check to verify that (potential) research subject name and mailing address are properly "matched". If discrepancies are found, a 100% accuracy check is required before letters may be mailed.
12. Use of Non-Standard Software ☑ I do NOT intend to use any new specialized software (i.e. Software that's not already approved OR installed) in this study.

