Stage/Aim 1: Refine the *Mobile Anger Reduction Intervention (MARI)* app in two successive cohorts of n=5 Veterans with PTSD and problematic anger. After the first cohort uses the application for a period of four weeks, a qualitative and quantitative evaluation will be conducted and each participant will be interviewed. Revisions will then be made based on these evaluations before another cohort of n=5 Veterans is treated. Again, following treatment an evaluation will be completed and further revisions will be made to the treatment. The resulting iteration of the treatment will be used in the subsequent pilot randomized controlled trial (Aim 2).

Stage/Aim 2: a) Evaluate the feasibility of recruitment, randomization, and retention procedures in a pilot study comparing MARI to a contact control condition (mindfulness app); and b) utilize psychophysiological and electronic diary monitoring to determine whether this assessment could be used as an outcome or mechanistic variable in a subsequent randomized clinical trial application focused on evaluating the efficacy of the MARI intervention. Aims 2a and 2b will be evaluated in a third cohort of 40 individuals with PTSD and self-reported problematic anger that will be randomized in a 1:1 ratio to MARI (n = 20) versus the mindfulness control condition (n = 20).

Design

The proposed research project is comprised of two stages. Each stage has its own aim. In the first stage (Stage/Aim 1) a successive cohort design (Epstein et al., 2007) will be used to refine the MIRA intervention two cohorts of 5 participants with PTSD and problematic anger. In the next stage (Stage/Aim 2), we will conduct a small, randomized controlled trial of MIRA compared to a mindfulness intervention (matched for time and participant contact) in a third cohort of 40 individuals.

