Stage/Aim 1: We propose to recruit two successive cohorts of 5 participants with PTSD and problematic anger. In each cohort, participants will come in to the laboratory for a pre-treatment visit. After establishing that they meet study criteria (including completion of a diagnostic interview to confirm PTSD diagnosis), they will complete some self-report questionnaires, and they will follow a think-aloud protocol (Jääskeläinen, 2010) during their initial use of the MARI intervention. They will then be asked to continue to use the mobile application five times weekly for the next four weeks. At the end of the first week of treatment, participants will be contacted over the phone to check in about whether they have encountered any problems with the app, answer any questions that they have, and remind them to use the app. After completing four weeks of treatment, each participant will return for a post-treatment visit during which they will provide feedback on their experience using the MARI application. These interviews will be audio-recorded. Their satisfaction with the MIRA intervention will be assessed with an in-depth interview about their impressions of the treatment (e.g. treatment dose, timing, and frequency; intervention content; text messaging; procedures). These interviews will ask them questions regarding how helpful they found the intervention and how useful and user-friendly they found the app. They will be asked to elaborate upon what aspects of the intervention and app they think are most and least helpful and to provide suggestions on how it could be improved. Data regarding their use of the application (e.g., frequency of use, timing of use) will also be collected.

Research Protocol, Version Date: 7/28/2022

Page 3 of 23

Based upon results, the intervention structure and content will be revised. The content that will be subject to revisions includes: the IBM content (e.g., topics and themes of scenarios); the MARI app structure and flow; the dose, timing, and frequency of the treatment sessions; and the methods used to promote treatment engagement and compliance.

After the intervention and study has been modified based on the information learned from the first cohort, we will treat a second cohort (n = 5). Again, we will use qualitative and quantitative data to refine that app in preparation for Stage 2 of the project.

Demographics and Background Measures	Time	Pre-	Post-	3-month
	(min)	treatment	treatment	follow-up
Demographics	2	•		

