Stage/Aim2: We propose to recruit 40 participants for the second stage of the study. Recruitment procedures and inclusion/exclusion criteria will be the same as those from Stage/Aim 1. After an initial phone screen, interested participants will come in for a pretreatment assessment. After confirming that they meet study criteria (including completion of a diagnostic interview to confirm PTSD diagnosis), they will complete baseline assessments (see assessment table above). If participants are eligible, they will sign a Duke informed consent form for the mobile health procedures of the study, which include wearing a portable heart rate monitor and using a smart phone for recording information about affect for 72 hours. After this baseline period, they will return the Duke equipment. They will then be randomized to either the MARI or mindfulness control condition (n = 20 per condition). Participants will be shown how to access their assigned intervention via Duke-owned smartphone. At the end of the first

Research Protocol, Version Date: 7/28/2022

week of treatment, participants will be contacted over the phone to check in about whether they have encountered any problems with the app, answer any questions that they have, and remind them to use the app. They will also complete a short interview about their impressions of the app at that point (see One Week Interview). They will be asked to continue to use the mobile application in the Duke study for the next four weeks. Next, they will do the ambulatory HRV monitor and electronic diary for a period

of 72 hours. Then, participants will return for an in-person, post-treatment visit. Finally, they will complete a three-month follow-up visit (see Figure 10 below).

Mobile Device Use

Study participants will access the MARI and mindfulness apps using Duke-owned mobile devices and a separate Duke IRB protocol is in place for this part of the study. These data collected with Duke-owned devices will be Duke-owned data, not VA-owned. This Duke-owned data will then be combined with VA data, and transferred via a VA-owned FIPS-encrypted thumbdrive or via VA's S.A.F.E.

Risk/Benefit Assessment

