is unaw_re." The participants fill in the missing letter of the word, forming the word "unaware," and assigning the benign interpretation. This interpretation is then reinforced by requiring the participants to correctly answer "yes" or "no" to a comprehension question (i.e., "Did this person hear you?"). In this example, they must answer "no" to proceed. Across treatment sessions, unique scenarios are presented (i.e., participants do not see the same scenario twice). Scenarios have been developed to capture a wide range of different themes that are likely to be anger-provoking. Themes include: physical aggression, driving situations, irritating traits of others, thinking you are being ignored by others, feeling argued with or criticized, thinking someone is stealing from you, having people block you, thinking that others have hostile feelings, feeling disrespected, thinking that people will not help you, thinking that others do not appreciate you, and thinking that situations are unfair. See Figure 7 for an example of a training scenario in the MARI app.

Figure 7. Example of a Training Scenario in MIRA App

For the purpose of this mobile application, we will be delivering the intervention daily for 4 weeks. The application will be programmed to include 28 treatments sessions that will each take approximately 10 minutes to

[figure not shown]
complete. Each session will include 42 training scenarios. No scenario will be repeated across these sessions. To this end, 1,176 unique training scenarios have been developed. Quantitative and qualitative data will be collected in Aim 1(b) to determine whether this treatment schedule and dosage of treatment is feasible and acceptable and adjustments will be made based on these data. Scenarios have been reviewed by 9 PTSD experts in the field and individuals with PTSD to confirm the content is relevant to this patient population. Additionally, the reading level has been assessed using an online readability calculator ("Readability Formulas") and all scenarios are at a 6th grade reading level or less. The app will time stamp use by the participants so that treatment time and completion for each participant can be calculated.

Figure 8. MIRA Application

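### Does a daily, 28-session schedule clash with the request for five uses a week in a way that affects the trial's results?

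*Combined protocol and SAP*

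**What the plan says.** The frequency of use appears in several places in the protocol.

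- **Study Interventions, MARI Intervention:** "we will be delivering the intervention daily for 4 weeks. The application will be programmed to include 28 treatments sessions". Each session holds 42 scenarios, none is repeated, and 1,176 have been written. Data from an Aim 1(b) are to "determine whether this treatment schedule and dosage of treatment is feasible and acceptable". The app time-stamps use so that each participant's treatment time and completion can be worked out.
- **Aims, Stage/Aim 1:** no part (b) is listed, but there is a matching step: "After the first cohort uses the application for a period of four weeks, a qualitative and quantitative evaluation will be conducted".
- **Design, Stage/Aim 1:** participants think aloud "during their initial use of the MARI intervention" at the first visit and are then "asked to continue to use the mobile application five times weekly for the next four weeks". "Data regarding their use of the application (e.g., frequency of use, timing of use) will also be collected". The items open to revision after each cohort include "the dose, timing, and frequency of the treatment sessions".
- **MARI Intervention, Additional content:** the congratulatory text message goes to those who keep to the suggested schedule, which is given as five or more sessions a week.
- **Design, Stage/Aim 2:** "They will be asked to continue to use the mobile application in the Duke study for the next four weeks", with no weekly number. The control arm is to match MARI in frequency and duration.
- **Data Analysis and Statistical Considerations:** the Stage 1 example of a revision takes five a week as the frequency that participants judge. For Stage 2, app utilization is one of four primary outcomes, all to be described.

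**The concern.** Read side by side, the intervention section names a daily schedule as the one to be assessed, while the people assessing it are asked for five uses a week. A Stage 1 report that the daily schedule was feasible would then rest on a request that nobody received.

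The second worry is carry-over into Stage 2. App utilization is a primary outcome there, and the protocol speaks of calculating completion for each participant without naming a base. If completion became a percentage, the same use could be reported in two ways. The control arm takes its frequency from MARI, so it would inherit the ambiguity.

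**Working it through.** **1. Reproduce the plan's own figures.** Daily use for four weeks is 7 × 4 = 28 sessions. With 42 scenarios each, 28 × 42 = 1,176, which is exactly the number said to have been written. So 28 is deliberate, and it fixes how much material had to be prepared if no scenario was to repeat.

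**2. Derive the Stage 1 request.** Five a week for four weeks is 5 × 4 = 20. The protocol does not print this number. The gap from the loaded content is 28 − 20 = 8 sessions.

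**3. See whether the statements can all hold together.**

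| Quantity | Value over four weeks | Where it stands |
|---|---|---|
| Sessions programmed | 28 | MARI Intervention |
| Suggested schedule | 20 or more (5 or more a week) | Additional content |
| Stage 1 request | 20 (5 a week) | Design, Stage/Aim 1 |
| Frequency judged in Stage 1 | 5 a week | Data Analysis, Stage/Aim 1 |

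A participant who completes between 20 and 28 sessions, with at least five each week, meets the suggested schedule and stays within the programmed content. One who does exactly five a week also matches the Stage 1 request. Only the word for daily delivery stands apart. It sits in a passage about what the app is programmed to supply.

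**4. See what each analysis uses.**

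- *Stage 1 (two cohorts of 5, so 10 people).* The inputs are interviews that cover dose, timing and frequency, the recorded frequency and timing of use, the average number of sessions completed, and individual graphs of weekly measures. None needs a target number of sessions. Because 28 sessions are loaded, use above five a week is possible and would be recorded.
- *Stage 2 (20 per arm).* App utilization is described. Sessions completed and minutes of use are taken from time stamps and do not depend on a target. The heart rate variability models as described use treatment, time and momentary anger, not session counts. No criterion for moving to a larger trial refers to 20 or 28.

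**5. Size the one conditional effect.** Assume that completion were reported as a percentage and that the Stage 1 frequency carried over to Stage 2. Neither is stated in the protocol. Then:

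- 20 sessions: 20/20 = 100%, or 20/28 = 71.4%
- 28 sessions: 28/20 = 140%, or 28/28 = 100%

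The ratio between the two bases is 28/20 = 1.40. It is a change of scale: participants keep the same order, and anyone who sees the count can convert one figure to the other.

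**The case for a change.** The strongest case for acting is that the compatible reading has to be inferred. The Stage 1 request has no wording to mark five as a minimum. The intervention section says daily, not up to daily, and one of the reminder suggestions is to set aside time every day. Staff could therefore brief participants differently. A primary outcome also deserves a stated metric, and a line or two would supply one without new data.

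Much of this stands as a comment on drafting. The sections do differ, and no sentence links them. The harm is harder to find. The claim that Stage 1 tests the wrong schedule treats daily use as something participants are told to do, and it equates an unlisted Aim 1(b) with Stage 1. The second step is reasonable; the first is not what the text says. Frequency is itself one of the things Stage 1 is meant to settle, so the starting figure is provisional.

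The missing metric for app utilization is a separate matter: it would exist even if every section gave the same frequency. Analysts would naturally fill it with sessions completed and minutes of use, which the app records. The control arm is described by two exercises and no session total, so counts and minutes are also the measures that apply to both arms alike.

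**Conclusion.** The inconsistency is in wording only, and no change to the plan follows. The protocol gives 28 sessions programmed, five or more a week suggested, and five a week requested in Stage 1. These figures can all hold at once. Followed as written, the plan yields sound counts, minutes and descriptive conclusions, and no sample size, estimate or decision rule turns on 20 versus 28. The largest numerical consequence is a factor of 1.40 in a percentage that the protocol does not say it will report.

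This rests on three assumptions: that 28 is the supply of sessions and not an instruction to complete them all; that utilization is reported as counts or time; and that the Stage 1 feasibility conclusion is worded for the frequency participants were asked to follow. The last two are what a careful analyst would do in any case. The sections on frequency should be reconciled as a clerical matter. Which frequency is intended is for the investigators to say, and this review takes no position on it.
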